### 11.1.5.1. Selinexor Dose Reduction for Decreased Glomerular Filtration Rate (GFR)

Selinexor is not significantly eliminated by the kidney; therefore, no dose alteration of selinexor is required with renal dysfunction. Creatinine clearance must be  $> 20$  mL/min in order to initiate therapy with Sd. If creatinine clearance declines during treatment and is believed to be unrelated to selinexor, the dose of selinexor may be maintained provided that the patient's condition is closely monitored. If creatinine clearances decline to  $< 20$  mL/min and this is felt to be related to selinexor, then the selinexor dose should be reduced by one level. If creatinine clearance returns to  $> 20$  mL/min for 4 weeks, then the dose of selinexor can be returned to previous level. If dialysis is implemented during Sd treatment, then Sd should always be given after dialysis.

#### 11.1.5.2. Selinexor Dose Adjustment in the Setting of Infection

Patients with active uncontrolled or suspected infections should have Sd treatment withheld until the infection has clinically resolved or the patient is clinically stabilized.

Dexamethasone should be adjusted per institutional guidelines, and adrenal suppression considered. After the infection has resolved clinically, or the patient's clinical condition has stabilized, treatment with selinexor may continue at the original dose. Missed doses will not be replaced. Patients may continue on antibiotics or other anti-microbial agents for prolonged periods while re-initiating their selinexor regimen at the discretion of the Investigator.

#### 11.1.5.3. Conditions Not Requiring Selinexor Dose Reduction

The following conditions are exceptions to the dose modification guidelines. Selinexor does not need to be held in the following cases:

- Alopecia of any grade
- Electrolyte or serum analyte (e.g., urate) abnormalities that are reversible with standard interventions

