**Table 6: Supportive Care and Dose Adjustment Guidelines**

**Please note the following recommendations:**

- After consultation with the Medical Monitor and at the discretion of the Investigator, selinexor dosing may be maintained for all hematological or non-hematological AEs that are NOT related to selinexor.
- For all selinexor-related AEs, if the prescribed dose reductions/interruptions in [Table 8](#) result in a stabilization of  $\geq 4$  weeks, a re-escalation may be considered after approval from the Medical Monitor.

Toxicity and Intensity	Selinexor Dose Modification
Fatigue (common)	
Grade 1 or Grade 2 lasting $\leq 7$ days	Maintain dose. Rule out other causes of fatigue, particularly dehydration and anemia. If found to be anemic, consider transfusing for hemoglobin $< 8$ g/dL. Institute supportive care medications per institutional guidelines and NCCN CPGO.  Patients with significant fatigue after several doses of selinexor may have an ongoing anti-tumor response. If fatigue is significant, consider assessment of tumor response as part of the patient's evaluation.
Grade 2 lasting $> 7$ days or Grade 3	Rule out other causes of fatigue, particularly dehydration and anemia. If found to be anemic, consider transfusing for hemoglobin $< 8$ g/dL. Institute supportive care medications per institutional guidelines and NCCN CPGO.  Interrupt selinexor dosing until resolved to Grade 1 or baseline.  For first occurrence, restart selinexor at current dose.  For $\geq$ second occurrence, reduce selinexor by 1 dose level when resuming selinexor. ( Table 5 ).  Patients with significant fatigue after several doses of selinexor may have an ongoing anti-tumor response. If fatigue is significant, consider assessment of tumor response as part of the patient's evaluation.

Toxicity and Intensity	Selinexor Dose Modification
Anorexia or Weight Loss	
Grade 1 anorexia Grade 1 weight loss Grade 2 anorexia	Maintain dose. Rule out other causes and consider a repeat nutritional consultation and nutritional supplements (e.g., Ensure®, Boost®, etc.). Institute supportive care medications per institutional guidelines and NCCN CPGO.

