Grade 2 weight loss Grade ≥ 3 anorexia or weight loss	Rule out other causes and consider a repeat nutritional consultation and nutritional supplements (e.g., Ensure®, Boost®, etc.). Institute supportive care medications per institutional guidelines and NCCN CPGO.  Interrupt dosing with selinexor until improves to Grade 1 or baseline and weight stabilizes, then reduce selinexor by 1 dose level when resuming selinexor (Table 5).  Consult Medical Monitor to discuss persistent or ≥ second occurrence of weight loss after stabilization.
Nausea, Acute (common)	
Grade 1 or 2 (If intolerable or persistent Grade 2 not responsive to supportive care, follow guidelines for Grade 3 below)	Maintain dose. Rule out other causes of nausea. Implement additional anti-nausea medications to supplement the protocol-required 5-HT3 antagonists using institutional guidelines and NCCN CPGO.
Grade 3	Rule out other causes of nausea. Implement additional anti-nausea medications to supplement the protocol-required 5-HT3 antagonists using institutional guidelines and NCCN CPGO.  Interrupt selinexor dosing until resolved to Grade ≤ 2 or baseline and restart selinexor at 1 dose level lower (Table 5).
Hyponatremia (common)	
Grade 1 (sodium levels < Normal to 130 mmol/L)	Maintain dose. Rule out other causes including drug (e.g., diuretic) effects. Be certain that reported sodium level is corrected for concurrent hyperglycemia (serum glucose > 150 mg/dL).  Treat hyponatremia per institutional guidelines including dietary review. Consider addition of salt tablets to patient's diet.
Grade 3 with sodium levels 120 to <130 mmol/L without symptoms	Correct for hyperglycemia as outlined under Grade 1. Treat hyponatremia per institutional guidelines. If (corrected) sodium is Grade ≤ 3 and continues to be asymptomatic, then patient may continue current dosing provided that intravenous saline and/or salt tablets (1-3 times daily) are provided.  If Grade 3 is persistent or worsens or does not respond to treatment, hold selinexor until resolved to Grade 1 or baseline and reduce selinexor by 1 dose level.
Grade 3 with sodium levels 120 to <130 mmol/L with symptoms or Grade 4 (<120 mmol/L)	Correct for hyperglycemia as outlined under Grade 1. Treat hyponatremia per institutional guidelines. Delay/hold selinexor until resolved to Grade 1 or baseline then reduce selinexor dose by 1 level (Table 5).

Toxicity and Intensity	Selinexor Dose Modification
Diarrhea (common)	

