Treat per institutional guidelines including blood transfusions and/or erythropoietins. Consider transfusing for any hemoglobin $< 8$ g/dL. If possible, maintain selinexor dose as long as patient is clinically stable, but if dose reduction or interruption is desired, discuss with the Medical Monitor.	
Other Selinexor-Related Adverse Events	
Grade 1 or 2	Maintain dose. Rule out other causes. Initiate treatment and/or standard supportive care per institutional guidelines.
Grade 3 or 4	
Rule out other causes. Interrupt selinexor until recovery to Grade <math>\leq 2</math> or baseline and reduce selinexor by 1 dose level.
 
Isolated values of Grade <math>\geq 3</math> alkaline phosphatase do NOT require dose interruption. Determination of liver versus bone etiology should be made, and evaluation of gamma-glutamyl transferase, 5'-nucleotidase, or other liver enzymes should be performed.

Abbreviations: 5-HT3 = 5-hydroxytryptamine; BIW = twice weekly; NCCN CPGO = National Comprehensive Cancer Network Clinical Practice Guidelines in Oncology; QW = once weekly

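### Protocol Section 11.1.5.3 excepts reversible electrolyte abnormalities without excluding sodium, which conflicts with the Table 6 hold for selinexor-related hyponatremia that is symptomatic Grade 3 or Grade 4

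*Protocol*

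**What the plan says.** Protocol Section 11.1.5.3 opens: "The following conditions are exceptions to the dose modification guidelines. Selinexor does not need to be held in the following cases". Two conditions follow. The first is alopecia, which is excepted at any grade. The second is "Electrolyte or serum analyte (e.g., urate) abnormalities that are reversible with standard interventions". Its only condition is reversibility.

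Table 6, titled "Supportive Care and Dose Adjustment Guidelines", gives hyponatremia its own rows:

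- **Grade 1:** dosing is maintained.
- **Grade 3 (sodium 120 to below 130 mmol/L) without symptoms:** if the corrected value is no worse than Grade 3 and the patient stays asymptomatic, "then patient may continue current dosing provided that intravenous saline and/or salt tablets (1-3 times daily) are provided". Otherwise, "If Grade 3 is persistent or worsens or does not respond to treatment, hold selinexor until resolved to Grade 1 or baseline", followed by a one-level reduction.
- **Grade 3 with symptoms, or Grade 4 (below 120 mmol/L):** after correction for hyperglycemia and treatment per institutional guidelines, "Delay/hold selinexor until resolved to Grade 1 or baseline then reduce selinexor dose by 1 level (Table 5", the reference being to the dose-level table.

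Table 6 ends with a row for "Other Selinexor-Related Adverse Events". For Grade 3 or 4 events it says "Rule out other causes. Interrupt selinexor until recovery to Grade" 2 or lower, or baseline, and then reduce by one level.

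Two further provisions set the scope. Section 11.1.5 and the opening notes of Table 6 allow dosing to be maintained for events not related to selinexor, at the investigator's discretion after consulting the Medical Monitor. Section 11.1.1 asks that dose modifications be discussed with the Medical Monitor before they are made.

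**The concern.** Sodium is an electrolyte, and hyponatremia is often corrected with saline or salt tablets. A patient with symptomatic Grade 3 or Grade 4 hyponatremia that the site expects to correct therefore falls under both texts. Table 6 says hold and then reduce. Section 11.1.5.3 says a hold is not needed, and its heading covers dose reduction as well.

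What is at stake is patient safety, not inference. The protocol gives a site a written basis to keep dosing through a toxicity that Table 6 says to hold for. Table 6 labels hyponatremia common, so the row is likely to be consulted. The Medical Monitor check in Section 11.1.1 is tied to making a dosing change, so a site that relies on the exception and changes nothing would not clearly trigger it.

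**Working it through.** The point turns on wording. The plan states no figure to reproduce.

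**Step 1: do the two texts overlap?**

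| Situation | Section 11.1.5.3 | Table 6 | Conflict? |
|---|---|---|---|
| Not related to selinexor | No hold needed if reversible | Dosing may be maintained after Medical Monitor consultation | No |
| Related, asymptomatic Grade 3, responds to treatment | No hold needed | May continue with saline and/or salt tablets | No |
| Related, asymptomatic Grade 3, persists, worsens or does not respond | Exception does not apply if not reversible | Hold, then reduce one level | No, if non-response is read as not reversible |
| Related, symptomatic Grade 3 or Grade 4, judged not reversible | Exception does not apply | Hold, then reduce one level | No |
| Related, symptomatic Grade 3 or Grade 4, judged reversible | No hold needed | Hold, then reduce one level | **Yes** |

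Only the last line conflicts. Table 6 makes the hold depend on response to treatment in the asymptomatic Grade 3 row and drops that condition in the more serious row. Section 11.1.5.3 brings it back for exactly those cases.

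**Step 2: does anything set precedence?** Section 11.1.5 points to Tables 5 and 6 but does not rank them against Section 11.1.5.3. Its concurrent-toxicity rule lets the most severe grade decide. That helps when the symptoms are themselves Grade 3 or 4 selinexor-related events. It does not help with milder symptoms or with asymptomatic Grade 4.

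**Step 3: how many patients?** Protocol Section 4.3.1.4 (N = 92) gives treatment-related hyponatremia as 33% overall and 18% Grade 3. For the Grade 3 count:

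- 16/92 = 17.4%
- 17/92 = 18.5%
- 18/92 = 19.6%

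Only 17 patients fits the stated 18%. The conflict group is the part of those 17 who were symptomatic, selinexor-related and judged reversible, plus any Grade 4 cases meeting the last two conditions. The documents give none of these shares and no Grade 4 rate, so the number cannot be estimated.

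**Step 4: what differs for one affected patient at the starting dose?** Table 5 gives 160 mg per week at the starting level and 120 mg per week one level down:

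(160 − 120)/160 = 25%.

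The two texts therefore differ by a hold and then a 25% lower weekly dose. Table 6 allows re-escalation to be considered after at least 4 weeks of stabilization, with Medical Monitor approval.

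**Step 5: does it reach the analysis?** The primary endpoint in SAP Section 4.1.1 is confirmed, centrally assessed response, and holds and reductions are not part of its definition. The counts of selinexor reductions and interruptions in SAP Sections 3.4.1 and 5.1.2.1 would reflect which text a site followed, but they are descriptive.

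**The case against.** The strongest defence is that the texts can be read together. Table 6 gives sodium a rule tiered by grade, symptoms and response. Section 11.1.5.3 is a general bullet whose only example is urate, and a specific rule ordinarily governs a general one. The exception also has an obvious purpose: without it, the catch-all row would interrupt dosing for any isolated Grade 3 or 4 analyte value. That row already exempts isolated alkaline phosphatase values, which shows the kind of case in mind. This reading is plausible and probably what was intended, and many sites would adopt it.

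It does not settle the text. The exception is written against the dose modification guidelines as a whole, and the sodium rows sit in a table titled as dose adjustment guidelines. Where the protocol wanted an exception confined to the catch-all row, as with alkaline phosphatase, it placed it inside that row.

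A reader might infer that the two texts give opposite orders. They do not: the exception is permissive, and a site that holds complies with both. A reader might also extend the conflict to all hyponatremia. The documents do not support that, because unrelated events have their own route through the Medical Monitor and asymptomatic Grade 3 that responds is handled consistently.

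**Conclusion.** The wording conflict stands in narrow form. It covers selinexor-related hyponatremia that is Grade 3 with symptoms, or Grade 4, and that a site judges reversible. Severity is minor. Confidence is medium, because a reasonable and probably intended reading removes the conflict even though the protocol does not state it.

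Frequency is unknown. A reader might apply the 18% to the roughly 130 Part 2 patients (0.18 × 130 ≈ 23) and treat the result as the number affected. The documents do not support this: the 18% counts all treatment-related Grade 3 cases, with no split by symptoms or reversibility. Nor can a useful Grade 4 count be obtained by subtracting Grade 3 from the overall figure. Section 4.3.1.4 reports hyponatremia as Grade 3 only, while giving Grades 3/4 together for thrombocytopenia and anemia, so the remainder may well contain no Grade 4 cases.

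Nothing here bears on the primary response-rate test or the sample size. The documents do not show that any site has misapplied the exception.

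**What to change.** Add one sentence to Protocol Section 11.1.5.3: *This exception does not apply to hyponatremia, which is managed per Table 6.* Send sites the same sentence as a clarification.

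The cost is one line in the protocol and one site communication, with no new procedures, visits or data. The exception keeps its probable purpose for urate and other analytes.

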#### 11.1.5.4. Missed or Vomited Doses

Note: A maximum of 2 doses of selinexor may be given per week.

##### Missed Doses

**If a dose was missed**, the schedule of that week should be altered to accommodate two doses in that week with at least 36 hours between two consecutive doses.

**If a dose must be skipped**, (e.g., due to recommendation of treating physician), the next dose will be taken as per schedule. Doses should not be administered less than 36 hours apart and all missed and delayed doses should be documented.

If a patient missed a full one or two-week period of dosing for non-study drug-related events (e.g., a required medical procedure or an unanticipated personal emergency), the days missed will be replaced. For example, if patient missed Cycle 2 Day 7 to Cycle 2 Day 14, then patient will start their next dosing on Cycle 2 Day 7 following the break. Similarly, if a patient misses Cycle 3 Day 1 to Cycle 3 Day 15, then the patient will start their next dosing on Cycle 3 Day 1. In this fashion, laboratory and radiographic assessments remain appropriate for timing of the administration of anti-cancer therapy.

##### Vomited Doses

If a dose is vomited  $\leq$  1 hour of ingestion, it will be replaced. If vomiting occurs  $>$ 1 hour after dosing, it will be considered a complete dose.

#### 11.1.5.5. Dose Escalation

In select cases (e.g., for patients showing stable disease or partial response and tolerating treatment particularly well), the selinexor dose may be increased by 20 mg after discussion with the Medical Monitor. However, in no case may the dose for any patient exceed 70 mg/m^2. Prior to any potential dose increase, the BSA for the patient should be calculated.

CCI

CCI Patients will be followed as long as possible or until disease progression and death.

## 11.2. Study Drug Storage

Selinexor tablets should be stored in a locked and secured area with access restricted to the site staff pharmacist or designee(s) at or below 86°F (30°C) (i.e., room or refrigerated temperature). Room temperature storage is preferred. The tablets should not be stored at freezer temperatures or frozen.

Selinexor tablets (20 mg) will be supplied in plastic film blisters with an aluminum foil lidding packaged in a secondary paper wallet with childproofing. See [Appendix 4](#) for detailed information on selinexor preparation, storage, stability, and administration.

Dexamethasone tablets should be stored as recommended on the product label.

## 11.3. Study Drug Accountability

The Investigator or designee must maintain an accurate record of the shipment and dispensing of study treatment (including lot/kit numbers) in a drug accountability log. Drug accountability will be noted by the clinical research associate (CRA) during site visits and at the completion of the study. Patients will be asked to return all unused study treatment and packaging on a regular basis, at the end of the study or at the time of study treatment discontinuation.

As appropriate during the course of the study, and at study close out, the Investigator will return all used and unused study treatment and a copy of the completed drug accountability log to the CRA.

Selinexor should not be used for any purpose outside the scope of this protocol, nor can selinexor be transferred or licensed to any party not participating in the clinical study. Data for selinexor are confidential and proprietary and shall be maintained as such by the Investigators.

The Investigator, or a responsible party designated by the Investigator, must maintain a careful record of the inventory and disposition of unused material.

All drug supplies provided by Karyopharm Therapeutics Inc. must be kept in an appropriate, limited access, secure place until used or returned to Karyopharm Therapeutics Inc. or designee for destruction. Drug supplies will be counted and reconciled at the site before being returned. The study site will be required to maintain a log of the temperature where the study medication is stored.

## 11.4. Concomitant Treatments

### 11.4.1. Required 5-HT3 Antagonists

In order to minimize nausea, unless contraindicated, all patients must receive 5-hydroxytryptamine (5-HT3) antagonists (ondansetron 8 mg or equivalent) starting before the first dose of selinexor and continued two or three times daily, as needed. Alternative anti-emetic agents may be used if the patient does not tolerate 5-HT3 antagonists.

#### **11.4.2. Supportive Care**

Supportive measures for optimal medical care should be provided during participation in this clinical trial. Based on clinical observations for 2103 adult patients evaluable for safety as of the 31 March 2017 safety data cutoff point, the main side effects associated with selinexor are primarily related to anorexia with poor caloric and fluid intake, fatigue, and nausea. Thrombocytopenia also occurs, although it is rarely associated with bleeding. In addition to dexamethasone included in the standard treatment plan, and required 5-HT3 prophylaxis (Section 11.4.1), supportive care including anti-nausea/anti-emetic therapy, acid suppression (proton pump inhibitors [PPI] and/or H2-blockers) and other treatments may be administered as described below:

- Appetite stimulants: megestrol acetate at a dose of 80-400 mg daily.
- Centrally acting agents: per National Comprehensive Cancer Network® [NCCN] Clinical Practice Guidelines® for antiemesis and anorexia/cachexia [palliative care])
- Neurokinin 1 receptor antagonist (NK1R antagonist): aprepitant or equivalent should be considered and will be covered for selected patients who have severe nausea and vomiting.

#### **11.4.3. Infection**

Appropriate broad-spectrum intravenous antibiotics and antifungal agents should be started immediately in patients who develop fever or other signs of systemic infection. Selinexor should be suspended in any patient with Grade 4 infection or clinical sepsis (in the absence of documented infection) until the condition is stabilized. Selinexor can then be re-started at the same dose.

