#### **11.1.5. Dose Reduction Guidelines for Toxicity**

Toxicity will be graded according to CTCAE v.4.03 criteria; the therapy modifications described below are applied according to this severity grading.

If more than one type of toxicity occurs concurrently, the most severe grade will determine the modification.

Re-escalation of the study drug is allowed as outlined in the sections that apply for the specific toxicity. If drug-related toxicity requires a treatment delay of more than 28 days, the patient is taken off protocol treatment.

Each dose modification or treatment delay must be documented in the eCRF, including the respective reason.

Based on observations from the ongoing Phase 1 studies in patients with advanced hematological and solid tumors, selinexor shows a reasonably wide therapeutic range, with activities from  $\sim 6$  mg/m^2 to  $\geq 60$  mg/m^2. Therefore, in order to optimize specific anti-tumor activity and the patient's tolerability, dose reductions and/or schedule modifications will be allowed as described in [Table 5](#) and [Table 6](#). Patients should also be treated aggressively with supportive care to reduce toxicities.

For all Grade  $\geq 3$  hematological or non-hematological AEs that are NOT selinexor related, after consultation with the Medical Monitor and at the discretion of the Investigator, selinexor dosing may be maintained, provided that the patient can continue to take the agent by mouth.

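### Protocol Sections 11.1.5.2 and 11.4.3 state different triggers for holding treatment in infection, and neither says which governs

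*Protocol*

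**What the plan says.** Two Protocol sections deal with infection.

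- **Section 11.1.5.2**, under the dose-reduction guidelines: "Patients with active uncontrolled or suspected infections should have Sd treatment withheld until the infection has clinically resolved or the patient is clinically stabilized". It sets no grade threshold. Sd is the protocol's term for the two drugs together. The section adds that dexamethasone is to be adjusted by institutional practice, with adrenal suppression in mind. Afterwards "treatment with selinexor may continue at the original dose".
- **Section 11.4.3**, under concomitant treatments: antimicrobials "should be started immediately in patients who develop fever or other signs of systemic infection". The hold comes only at a higher level: "Selinexor should be suspended in any patient with Grade 4 infection or clinical sepsis", where sepsis is qualified as being without a documented infection. Dexamethasone is not mentioned. Once the patient is stable, "Selinexor can then be re-started at the same dose".

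More general rules overlap with these.

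- **Section 11.1.5**, for Grade 3 or higher events not related to selinexor: after consulting the Medical Monitor and at the Investigator's discretion, "selinexor dosing may be maintained, provided that the patient can continue to take the agent by mouth".
- **The notes heading Table 6** give the same permission for unrelated events without a grade limit.
- **Table 6, last block**, for selinexor-related events without their own row: maintain the dose at Grade 1 or 2. At Grade 3 or 4, interrupt until Grade 2 or lower "or baseline and reduce selinexor by 1 dose level".

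None of these general rules makes an exception for infection.

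**The concern.** A site that looks up infection can land on either section. One tells it to withhold both drugs whenever an infection is uncontrolled or merely suspected. The other, whose heading is simply Infection, gives an explicit suspension threshold of Grade 4 or clinical sepsis. A reader of that section alone would find no instruction to hold for a less severe infection.

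This is a patient-safety instruction in a regimen that includes a glucocorticoid, so the hold rule should read the same wherever it is found. There is a secondary reporting consequence. SAP Section 3.4.1 counts patients with interruptions of each drug separately, and Section 5.1.2.1 tabulates events leading to reduction or interruption of each drug. If sites apply different triggers, those tables will partly reflect which section a site followed.

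**Working it through.** No figure in the plan bears on this point, so the check is a comparison of the rules by type of case.

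| Case | Section 11.1.5.2 | Section 11.4.3 | General rules (11.1.5, Table 6) |
|---|---|---|---|
| Uncontrolled or suspected infection, Grade 1-2, no sepsis | Withhold Sd | No hold stated | May be maintained if unrelated; dose maintained if selinexor-related |
| Same, Grade 3, not related to selinexor | Withhold Sd | No hold stated | May be maintained after consultation |
| Same, Grade 3, related to selinexor | Withhold Sd | No hold stated | Interrupt, then reduce one level |
| Grade 4 infection, or clinical sepsis | Withhold Sd | Suspend selinexor | As above, by grade and relatedness |
| Restart dose | Original dose | Same dose | One level lower if related and Grade 3 or 4 |

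Reading down the table:

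1. **Trigger.** The two infection sections differ in the first three rows. In the third, Table 6 interrupts selinexor anyway, so a hold follows whichever infection section is read. The real gap is the first two rows.
2. **Drug held.** In the fourth row both sections stop selinexor, but one names Sd and the other selinexor only. In practice the difference is smaller than it looks, because Sections 11 and 11.1.3 give dexamethasone with each selinexor dose. A selinexor hold would ordinarily take the accompanying dexamethasone dose with it, but Section 11.4.3 does not say so.
3. **Restart.** The infection sections agree with each other: both allow restart on stabilization, at an unchanged dose. They differ from the Table 6 catch-all, which lowers the dose after a related Grade 3 or 4 event. No text says whether infection is exempt from that row.
4. **Precedence.** Neither infection section cites the other, and the general rules do not defer to them.

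**The case against.** The strongest case against is that this is not a true contradiction. A reader might infer that the protocol holds a patient under one section and orders dosing under the other. The text does not support that: Section 11.4.3 is silent below Grade 4 and does not direct a site to continue. A site that follows Section 11.1.5.2 breaches nothing in Section 11.4.3. The headings also help, since Section 11.1.5.2 is titled as the dose-adjustment rule for infection, while Section 11.4.3 sits under concomitant treatments and opens with antimicrobials. Section 11.1.1 further asks that dosing changes be discussed with the Medical Monitor first.

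Most of this stands, and it limits the point to different stated triggers. It does not remove it. An explicit threshold in a section called Infection is easily taken as the study's threshold. The permission to maintain dosing for unrelated events points the same way and does not exclude infection. Medical Monitor discussion is prompted when a site proposes a change; under Section 11.1.1, a site that sees no reason to change has nothing to raise.

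The analytic effect is also fairly described as small. The interruption and exposure outputs are descriptive. SAP Section 3.4.2 leaves doses missed through treatment interruption out of the prescribed count, so a hold does not lower selinexor compliance or remove a patient from the per-protocol population.

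**Conclusion.** The inconsistency is real and should be corrected. It concerns the hold trigger and the drug or drugs held, not the restart dose in the two infection sections. It bites mainly for Grade 1-2 infections, and for Grade 3 infections not related to selinexor, without sepsis, and only at a site that does not apply Section 11.1.5.2. A reader might infer that every infection below Grade 4 is affected. That is too broad: clinical sepsis triggers suspension in Section 11.4.3 without a grade, and related Grade 3 events are interrupted under Table 6.

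The number of patients affected cannot be given, because the documents report no infection rate. A reader might take the 19% rate of Grade 3 or higher neutropenia in Protocol Section 4.3.1.4 as a proxy for Part 1. It should not be used. It comes from preliminary study data on 92 patients, while Part 1 enrolled 79, so at least 92 − 79 = 13 of them are outside Part 1. Neutropenia is not infection, and Grade 3 or 4 neutropenia has its own interruption rule in Table 6, with or without fever.

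The primary ORR analysis is not affected. The conclusion rests only on current protocol text and takes no view on which clinical rule is right.

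**What to change.** Reconcile Sections 11.1.5.2 and 11.4.3 so that one stated rule governs which infections trigger a hold and which drug or drugs are held, and cross-refer between the sections. State how that rule relates to the permission to maintain dosing for unrelated events in Section 11.1.5 and the Table 6 notes, and to the Table 6 row for other selinexor-related events. The clinical team decides the content. The cost is a wording change in the protocol and a memo to sites; no analysis changes.
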